7.3.3 TIME PERIOD AND FREQUENCY FOR EVENT ASSESSMENT AND FOLLOW-UP

AE review and evaluation will occur at every study visit prior to drug administration once a month, including the final visit, which will be one month after the final medication dose is administered.

7.3.4 ADVERSE EVENT REPORTING

AEs will be reported by the patient throughout the entire study period study, including during study visits. All AEs, regardless of seriousness, severity, or presumed relationship to study therapy, will be recorded using medical terminology in the source document and on the case report form (CRF). Whenever possible, diagnoses will be given when signs and symptoms are due to a common etiology (e.g., cough, runny nose, sneezing, sore throat, and head congestion should be reported as "upper respiratory infection"). Investigators will record on the CRF their opinion concerning the relationship of the AE to study therapy and/or device (pre-filled syringe).

Any non-serious AE that occurs after the dose of study drug will be documented on a CRF page and followed until resolution, stabilization, or the End-of-Study Visit at Day 180 (Visit 8). Any SAE that occurs after the dose of study drug (regardless of relationship to study drug) will be followed until the event resolves, stabilizes, or becomes non-serious. The description of the AE will include type of event, date and time of onset, date and time of resolution, blinded investigator-specified assessment of severity and relationship to study drug, time of resolution of the event, seriousness, any required treatment or evaluations, and outcome.

7.3.5 SERIOUS ADVERSE EVENT (SAE) REPORTING

All serious AEs (SAEs) during the study period will be documented and reported to Amgen within 72 hours using Amgen's electronic reporting form, in addition to being reported to the Duke University Health System IRB and other institutional regulators, as applicable. Furthermore, changes in an already

reported serious AE will be reported to Amgen within 72 hours. The investigator will not be responsible for AEs occurring after the study period. Appendix A contains Amgen's Safety Data Exchange Requirements.

The sponsor-investigator will report suspected unexpected serious adverse reaction to the FDA in accordance with 21 CFR 312.32. The FDA will be notified of any unexpected fatal or life-threatening suspected adverse reactions no later than 7 calendar days after notification. Any other SAE that is possibly related and unexpected will be reported to the FDA no later than 15 calendar days upon notification of the event.

The FDA Medwatch Form 3500A will be used to report all SAEs. The MedWatch 3500A form is available at:

- <https://www.fda.gov/downloads/AboutFDA/ReportsManualsForms/Forms/UCM048334.pdf>

Instructions for the MedWatch 3500A form are available at:

<https://www.fda.gov/downloads/AboutFDA/ReportsManualsForms/Forms/UCM295636.pdf>

SAEs will be reported to the Duke University Health System Institutional Review Board (IRB) per their policy, "Problems or Events that Require Prompt Reporting to the IRB".

7.3.6 REPORTING EVENTS TO PARTICIPANTS

Subjects will be informed of any adverse events that may affect their rights, welfare and/or decision to continue study participation via the consent process and signing the consent (all subjects will receive a signed/dated copy of the consent form).

7.3.7 REPORTING OF PREGNANCY

Pregnancies occurring after the first dose of investigational product will be reported as a serious adverse event and will result in unblinding. The investigator will report within one working day of knowledge of the pregnancy to the IRB. Following delivery or termination of pregnancy, a follow-up pregnancy report will be completed. Spontaneous abortions will be reported as SAEs.

7.3.8 UNBLINDING

In the event of an SAE that requires unblinding of the patient to determine whether they are on the active study drug, the PI or coordinator will contact the IDS Pharmacy for emergency unblinding at

[contact].

The subject will be removed from the study at that point.

7.4 UNANTICIPATED PROBLEMS

7.4.1 DEFINITION OF UNANTICIPATED PROBLEMS (UP)

An unanticipated problem (UP) is defined as an adverse event that is unexpected given the information currently known about the medication and, to a reasonable extent, may be related to participation in the study. Moreover, an UP can potentially indicate greater risk to all participants than was initially anticipated.

7.4.2 UNANTICIPATED PROBLEM REPORTING

UPs will be reported to Amgen within 24 hours and to the investigator's IRB. Changes may be made to the research protocol and informed consent document, or the study may be suspended based on an UP.

7.4.3 REPORTING UNANTICIPATED PROBLEMS TO PARTICIPANTS

After review by Amgen and the investigator's IRB, subjects may be notified of UPs as well as any changes in the protocol that warrant a change to the consent form.

7.4.4 STUDY MONITORING

The study will be monitored by Duke University Department of Surgery staff in accordance to the Duke "Clinical Quality Management Plans" Policy.

8.1 STATISTICAL HYPOTHESES

- Primary Efficacy Endpoint(s):
 - ε To compare change from baseline in mean number of days per month with significant pain or pressure between treatment and placebo groups at 4 to 6 months.

Null Hypothesis: In subjects with idiosyncratic facial pain mimicking rhinosinusitis, the erenumab treatment group is the same as placebo, in terms of the reduction from baseline in mean monthly days with significant pain at months 4 to 6.

Alternative Hypothesis: In subjects with idiosyncratic facial pain mimicking rhinosinusitis, the erenumab treatment group is different than placebo, in terms of the reduction from baseline in mean monthly days with significant midfacial pain at months 4 to 6.

- Secondary Efficacy Endpoint(s):

- ⊖ To compare change from baseline in mean number of days per month with significant pain or pressure between treatment and placebo groups at 1 month and 3 months.
- To compare change in mean number of days per month with significant facial pain between baseline and 1, 3, and 4-6 months within each group
- To compare change in 22-Item Sinonasal Outcomes Test (SNOT-22) between treatment and placebo groups at 1, 3, and 6 months
- To compare change in the Migraine Functional Impact Questionnaire (MFIQ) and its five subdomains between treatment and placebo groups at 1, 3, and 6 months
- To compare change in reduction of rescue medication use between treatment and placebo groups at 1, 3, and 4-6 months
- ⊖ To compare change in the mean number of days per month with significant congestion and rhinorrhea between treatment and placebo groups at 1, 3, and 4-6 months.
- To compare reduction in mean pain score between treatment and placebo groups at 1, 3, and 4-6 months

8.2 SAMPLE SIZE DETERMINATION

The primary endpoint is the change from baseline to 4-6 months in the average number of days per month with significant mid-facial pain. Assuming a treatment effect compared to placebo of -3.0 and a common standard deviation of 3.5, a sample size of 33 subjects per group would provide 90% power using a two-sample t-test with a 2-sided significance level of 0.05. An assumed 10% dropout is factored into the sample size calculation.

8.3 POPULATIONS FOR ANALYSES

The complete analysis dataset includes all subjects randomized in the study. Summaries of demographic data, baseline disease characteristics, and subject disposition will utilize this dataset.

The efficacy dataset will be used to carry out analyses of all primary and secondary endpoints. This dataset includes all randomized patients who received at least one dose of the randomly assigned treatment regimen and had at least one post-baseline measurement for mid-facial pain days per month.

8.4 STATISTICAL ANALYSES

8.4.1 GENERAL APPROACH

The primary objective of this study is to evaluate the efficacy of erenumab compared to placebo on the change from baseline in mean monthly days with significant facial pain, in subjects with midfacial pain or pressure mimicking rhinosinusitis.

The primary analysis will be performed when the last randomized subject completes the 6 month (day 180) study visit assessment or is discontinued from the study.

Subjects will be analyzed based on their randomized treatment group assignment. This will be an intention to treat analysis.

Descriptive statistics by treatment group will be tabulated at each study visit. For continuous endpoints, descriptive statistics include: number of subjects, mean, median, standard deviation, standard error, lower and upper quartiles, minimum and maximum. For categorical endpoints, frequency and percentage will be provided.

8.4.2 ANALYSIS OF THE PRIMARY EFFICACY ENDPOINT(S)

The change in the number of days with facial pain or pressure from baseline to completion of the six-month treatment administration period will be analyzed using a linear mixed-effects model including treatment group, baseline value, scheduled visit, and the interaction of treatment with scheduled visit. Imputation is not planned. If applicable, a first-order autoregressive covariance structure is assumed. Least squares means for each treatment group, standard errors, associated 95% confidence intervals as well as the treatment difference, associated 95% confidence intervals and p-values will be reported. A two-sided significance level of 0.05 is assumed.

Additionally, we will compare the change in the mean number of days per month with significant idiosyncratic facial pain between the treatment group versus the placebo-controlled group from baseline to intermediate time points at one and three months.

8.4.3 ANALYSIS OF THE SECONDARY ENDPOINT(S)

- The mean number of days per month with significant pain or pressure

This will be compared between baseline and 1, 3, and 4-6 months within each group. This represents an intragroup analysis as opposed to comparing treatment and placebo groups.

- 22-Item Sinonasal Outcomes Test (SNOT-22)

The change in mean scores from baseline for the SNOT-22 survey will be compared at 1, 3, and 6 months. The SNOT-22 is the most widely-used validated sinonasal questionnaire in the otolaryngologic literature.[16] Respondents rate the severity of twenty-two symptoms from a scale of 0 (no problem) to 5 (severe as can be) over the previous two weeks, for a score ranging from 0 to 110. It is self-administered and includes symptoms pertaining to multiple domains, including nasal, extranasal, sleep, and psychological. A minimal clinically important difference has been determined to be 9.[17] Analysis of the SNOT-22 will allow the assessment of changes in specific sinonasal symptoms, such as drainage and congestion, which are thought to be associated with idiosyncratic facial pain.

- Migraine Functional Impact Questionnaire (MFIQ)

The change in mean scores from baseline for each of the five subdomains of the MFIQ will be compared at 1, 3, and 6 months. The MFIQ is a self-administered 26-item questionnaire assessing the impact of migraine on five domains over the previous seven days: physical functioning (5 items), usual activities (10 items), social functioning (5 items), emotional functioning (5 items), and overall functioning (1 item).[18,19] Each item is rated on a 5-point scale, with 5 representing the greatest impact. The scores for each domain will be calculated as the sum of the items.

- Change in number of doses of rescue medication use for facial pain

The change in number of doses of rescue medication use from baseline to 1, 3, and 4-6 months will be compared. The daily data log will enable analysis of frequency, type, and numeric dose of the following rescue medications: triptans, opiates, tramadol, acetaminophen-containing medications, butalbital, antihistamines, non-steroidal anti-inflammatory drugs, decongestants, antibiotics, and steroids. The frequency (number of doses) of rescue medication use will be compared between the two groups at baseline and 1, 3, and 4-6 months

- Mean daily pain score

The change in mean daily pain score (scale of 0 to 10) will be compared between the treatment and control groups from baseline to 1, 3, and 4-6 months.

- Mean number of days per month with significant congestion and rhinorrhea

Significant congestion and rhinorrhea will be defined as symptom score greater than 4 out of 10. The change in mean number of days per month with significant congestion and rhinorrhea from baseline to 1, 3, and 4-6 months will be compared for treatment and control groups.

Analysis of the secondary endpoints will be performed using the same methods as the primary endpoint.

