1.4 OBJECTIVES AND ENDPOINTS

OBJECTIVES	ENDPOINTS
Primary:	
To compare change from baseline in mean number of days per month with significant pain or pressure between treatment and placebo groups at 4-6 months.	Change in mean number of days per month with significant midfacial pain or pressure (defined as greater than 4/10) from baseline to 4-6 months
Secondary:	
To compare change from baseline in mean number of days per month with significant pain or pressure between treatment and placebo groups at 1 month and 3 months.	Change in mean number of days per month with significant midfacial pain or pressure (defined as greater than 4/10) from baseline to 1 month and 3 months.
To evaluate the efficacy of erenumab in reducing mean number of days with facial pain (intragroup change)	Change in mean number of days per month with significant pain or pressure comparing baseline to 1, 3, and 4-6 months within each group.
To evaluate the efficacy of erenumab in reducing burden of rhinosinusitis symptoms	Change in 22-Item Sinonasal Outcomes Test (SNOT-22) questionnaire score from baseline to 1, 3, and 6 months
To evaluate the efficacy of erenumab in improving functional impact of migraine-related facial pain	Change in each of the five domains of the Migraine Functional Impact Questionnaire (MFIQ) from baseline to 1, 3, and 6 months
To evaluate the efficacy of erenumab in improving associated symptoms of nasal congestion and rhinorrhea	Change in average number of days per month with significant nasal congestion or rhinorrhea (defined as greater than 4/10) from baseline to 1, 3, and 4-6 months
To evaluate the efficacy of erenumab in reducing pain medication usage	Change in doses of rescue pain medications taken from baseline to 1, 3, and 4-6 months
To evaluate the efficacy of erenumab in reducing daily pain severity	Change from baseline in mean daily pain score from baseline to 1, 3, and 4-6 months

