During the screening visit, eligible subjects will receive instructions and training on use of the ecological momentary assessment (EMA) via mobile phone. If for any reason they cannot complete the EMA via a mobile phone, a paper copy will be available to the participant. During the 30-day lead-in period, subjects will be expected to score on a scale of 1 to 10 their symptoms of pain/pressure, nasal congestion, and rhinorrhea as well as any rescue medicines taken for pain each day. Subjects will be instructed to return to the site at the end of the 30-day lead-in period for Visit 2. During the 30-day lead-in period, subjects must record a minimum of 20 (67%) daily diary entries to be eligible for randomization during visit 2. This will be evaluated through the review of the EMA daily data log. The coordinator may call subjects to remind them to complete the log during this time period. Subjects who do not have a minimum of 20 daily entries will be considered a screen failure and removed from the study.

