4.3 SCREEN FAILURES

Screening will occur at the baseline visit. Up to twenty screen failures are anticipated. The reason for screen failure will be documented.

Screen Failures are defined as:

- a) Patients who are not compliant with EMA or daily diary for more than 33% of triggered queries during the 30-day lead-in period.
- b) Patients who do not report at least 10 days of significant pain or pressure during the 30-day lead-in period.
- c) Patients needing prophylactic migraine medicine (meds listed under exclusion # 6) during the 30 day lead-in period.

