5.5 CONCOMITANT THERAPY

5.5.1 RESCUE MEDICINE

Rescue medicine for facial pain will be permitted. Recommendations by the principal investigator may consist of over-the-counter medications such as antihistamines, non-steroidal anti-inflammatory drugs, decongestants. Antibiotics and steroids may be indicated if clinical evidence for sinusitis exists. Patients will be referred to their primary care provider (PCP) for prescription medications including triptans, opiates, tramadol, acetaminophen-containing medications, butalbital. These medications are not commonly prescribed by otolaryngologists, and therefore, should be managed by the PCP. Subjects will be instructed to record rescue medicine intake in their EMA data log. The study coordinator or study team member will review all recorded rescue meds and query the patient regarding any rescue meds prescribed by another health care provider. The study coordinator or study team member will verify the rescue medications, by either review of the pill bottle or call to the PCP.

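### Section 8.4.3 lists antibiotics and steroids in a dose count that the objectives define as rescue pain medication, although Section 5.5.1 mentions those two classes only in connection with sinusitis

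*Combined protocol and SAP*

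**What the plan says.** The objective in Section 1.4 is "To evaluate the efficacy of erenumab in reducing pain medication usage", and the endpoint beside it is "Change in doses of rescue pain medications taken from baseline to 1, 3, and 4-6 months". The synopsis (Section 1.1, item 3d) also refers to rescue pain medications.

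Section 8.4.3 heads the endpoint as rescue medication for facial pain. It says the daily log will support analysis of how often, what type and how much was taken of ten classes: "triptans, opiates, tramadol, acetaminophen-containing medications, butalbital, antihistamines, non-steroidal anti-inflammatory drugs, decongestants, antibiotics, and steroids". It then states the comparison: "The frequency (number of doses) of rescue medication use will be compared between the two groups at baseline and 1, 3, and 4-6 months". No class is weighted, excluded or given its own analysis. The section closes by applying the primary-endpoint method to the secondary endpoints.

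Section 5.5.1, on rescue medicine for facial pain, names antihistamines, NSAIDs and decongestants as possible recommendations. Of the other two classes it says "Antibiotics and steroids may be indicated if clinical evidence for sinusitis exists".

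The diary instructions differ in scope. Section 5.5.1 says "Subjects will be instructed to record rescue medicine intake in their EMA data log". The lead-in text in Section 3.2.1 asks for daily symptom scores "as well as any rescue medicines taken for pain each day".

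**The concern.** An endpoint meant to show reduced use of pain medication should count medication taken for pain. The protocol's own text links antibiotics and steroids to a different condition, one that the endoscopy and imaging entry criteria (Section 4.1) are designed to rule out at enrolment. These drugs usually come as courses of many scheduled doses, so a few infections could move the arm means and widen the spread.

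Interpretation is at stake first. Even a clear difference on the pooled count could not be read as less pain medication without knowing how many doses were given for sinusitis. Some loss of power comes second. If the choice of classes is left open until after unblinding, the definition could also be chosen with the results in view.

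**Working it through.** **1. The text.** The objectives say pain medication. The analysis section lists ten classes, including two that the rescue section mentions only for sinusitis. The facial-pain heading in 8.4.3 and the narrower diary wording in 3.2.1 point towards pain medication only, but neither removes the two classes from the list. The two diary wordings may also lead some participants to log an antibiotic course and others not to, which makes the count inconsistent.

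**2. The plan's own figures.** There is none for this endpoint. The primary-endpoint figure in 8.2 (difference 3.0, SD 3.5, 90% power, two-sided 0.05) reproduces: 2 × (1.960 + 1.282)² × 3.5² / 3.0² = 28.6, so 29 per arm, and 29 / 0.90 = 32.2, so 33. It does not depend on this point. After 10% dropout, 33 × 0.90 = 29.7, so 30 per arm is used below.

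**3. A course against a month of analgesics (assumed counts).** Courses of 5, 7, 10 or 14 days at 1 to 3 doses a day give 12 patterns of 5 to 42 doses. Analgesics on 10, 15, 20 or 30 days a month at 1 to 3 doses a day give 10 to 90 doses. The 10-day floor matches the entry rule in 4.3, which screens out "Patients who do not report at least 10 days of significant pain or pressure during the 30-day lead-in period". The course is larger in 25 of 144 combinations:
- at 10 analgesic doses a month, 8 of 12 course patterns;
- at 20 doses, 4 of 12;
- at 30 doses, 1 of 12;
- at 45 or more, none.

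**4. Effect on an arm mean.** One 20-dose course in one of 30 participants moves that arm's mean by 20 / 30 = 0.67 doses in a single month, or 0.67 / 3 = 0.22 doses when averaged over months 4 to 6. The month 1 and month 3 comparisons are therefore the more exposed.

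**5. Effect on power (all inputs assumed).** Take an SD of change of 6 doses, where change is the mean of three follow-up months minus one baseline month, and a true effect of -4.5. The monthly within-subject variance v then satisfies v × (1 + 1/3) = 36, so v = 27. A 20-dose course with probability p in any month adds 400 × p × (1 − p). At p = 5% this is 19, so v = 46.

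With between-subject SD s, the residual variance of the three-month mean given baseline is

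R = s² + v/3 − s⁴ / (s² + v),

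and the standard error of the difference is √(R × 2/30). Power from the noncentral t distribution with 57 degrees of freedom:

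| s | R, no courses | Power | R, 5% courses | Power | Loss (points) |
|---|---|---|---|---|---|
| 3 | 15.75 | 99.1% | 22.86 | 94.8% | 4.3 |
| 5 | 21.98 | 95.5% | 31.53 | 86.2% | 9.3 |
| 8 | 27.99 | 89.9% | 42.10 | 75.2% | 14.7 |

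Simulation under the same inputs gave losses of about 3 to 14 points, which agrees to within about a point. At p = 3% (v = 38.64; R = 20.18, 28.06, 36.97) power is 96.8%, 89.9% and 80.4%. At p = 10% (v = 63; R = 28.88, 38.90, 52.75) it is 89.0%, 78.4% and 65.5%.

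This approximates the planned model: it adjusts for baseline, but it summarises follow-up as one mean and does not fit the visit terms or the autoregressive structure.

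**The case against.** **The plan never says the ten classes are summed.** This is literally true. The list describes what the log can support, by type, and the heading, Section 1.4 and the lead-in diary text all speak of pain. A careful analyst might leave sinusitis courses out. However, the list is introduced as the rescue medications, the comparison is of number of doses of rescue medication, and no breakdown by class is specified. A pooled count is the plain reading, and an endpoint should not depend on the analyst departing from it.

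**Antibiotic use matters to this trial.** The executive summary gives antibiotic overuse as a motivation, so collecting these doses is sensible. That supports reporting them on their own, where they can be seen, rather than mixing them with analgesics.

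**Courses may be rare.** Entry requires a clean endoscopy and near-clear imaging, so 5% of participant-months may be too high, especially in the lead-in month. This stands, and it is why the power figures are only illustrative.

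**The stakes are limited.** This is one of many secondary endpoints, and type is recorded, so a breakdown could be produced later. Both are true, but a breakdown chosen after unblinding carries less weight than a definition fixed beforehand.

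Three stronger readings are tempting, and the documents do not support them:
- A reader might infer that antihistamines and decongestants are misplaced too. Section 5.5.1 names both as rescue for facial pain, so counting them agrees with the protocol.
- A reader might infer a much larger power loss. An unadjusted t-test on change, with the inputs above, falls from 82% to 59% as the SD rises from 6 to √(46 × 4/3) = 7.83. But Sections 8.4.2 and 8.4.3 plan a model that includes baseline. Three quarters of the added variance in the t-test comes from courses in the single baseline month; with none there, the t-test itself gives 75%.
- A reader might infer that the protocol restricts antibiotics and steroids strictly to sinusitis. The wording is permissive, although sinusitis is the only circumstance it gives for them.

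**Conclusion.** The point holds as a mismatch between Sections 1.1 and 1.4, 5.5.1 and 8.4.3 over antibiotics and steroids. Followed as written, 8.4.3 yields a count that does not measure the stated objective. This conclusion rests on the text alone.

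The size is less certain. At a 5% course rate, a baseline-adjusted analysis loses roughly 4 to 15 points of power for between-subject SDs of 3 to 8. Over course rates of 3% to 10%, the loss runs from about 2 points (99.1% to 96.8%) to about 24 (89.9% to 65.5%). The course length, course rate, SDs and effect are all assumed. It would be too strong to say that one infection generally outweighs a month of analgesic use: that holds for low users, including participants whose use falls during the trial, and not for heavy daily users.

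The point should be corrected, but it concerns a secondary endpoint. The primary endpoint and sample size are unaffected.

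**What to change.** Before unblinding, amend Section 8.4.3 to say that antibiotics and steroids do not enter the rescue pain-medication dose count, and that their doses are reported separately by arm. Keep antihistamines and decongestants in the count, in line with Section 5.5.1. Optionally, pre-specify a sensitivity analysis restricted to analgesics and triptans.

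The change affects only the definition used in the analysis. Medication type is already logged, so the diary stays as it is, and rescue treatment itself is unchanged. The cost is a few lines of SAP text and one extra descriptive table.

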1 PROTOCOL SUMMARY

1.1 SYNOPSIS

Title: A Randomized, Double-Blinded Single Site Study to Evaluate the Efficacy of Erenumab for Treatment of Idiosyncratic Facial Pain Mimicking Rhinosinusitis

Study Description:

Objectives: Primary Objective: To compare change from baseline in mean number of days per month with significant pain or pressure between treatment and placebo groups at 4 to 6 months.

Secondary Objectives:

1. To compare change from baseline in mean number of days per month with significant pain or pressure between treatment and placebo groups at 1 month and 3 months.

2. To compare mean number of days per month with significant pain or pressure comparing baseline to 1, 3, and 4 to 6 months within each group (intragroup analysis)
3. To compare change from baseline between treatment and placebo groups at 1, 3, and 4 to 6 months for the following:

- a. Sinonasal Outcome Test-22 (SNOT-22)
- b. Migraine Functional Impact Questionnaire (MFIQ)
- c. Mean number of days per month with significant nasal congestion and rhinorrhea.
- d. Doses of rescue pain medications taken
- e. Mean daily pain score

Study Population: Patients presenting with at least three months of chronic or episodic midfacial pain or pressure referred for evaluation of sinusitis and found to have no endoscopic or radiographic evidence of sinusitis

[figure not shown]
Phase: IV

Description of Sites/Facilities Enrolling Participants: Duke University Health System

Description of Study Intervention: Erenumab vs. Placebo

Study Duration: 34 months
Participant Duration: 7 months

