2.2 BACKGROUND

Approximately 30 million adult Americans, or 12% of the US population, are diagnosed with rhinosinusitis (RS) annually and antibiotics are prescribed in 82% of associated office visits. This includes patients with acute rhinosinusitis (ARS), in which symptoms last <4 weeks, recurrent acute rhinosinusitis (RARS), in which a patient has 4 or more acute episodes in a year, and chronic rhinosinusitis (CRS), in which symptoms last >12 weeks [6]. However, several studies suggest that many of these patients have no objective evidence of sinusitis on endoscopy or imaging, but rather meet criteria for migraine or other

primary headache disorder.[1, 5-8] This leads to ineffective treatments and associated morbidity, such as antibiotic resistance, persistent symptoms, and unnecessary surgery.

Patients with idiosyncratic facial pain may actually have chronic upregulation of any one or more branches of the trigeminal nerve leading to the perception of facial pressure and pain with secondary autonomic symptoms such as nasal congestion, rhinorrhea, tearing, and facial swelling. In other words, they may have a complex spectrum of nervous system dysfunction that can mimic RS. Despite this, studies have demonstrated that patients undergo invasive sinus procedures at least in part due to the lack of effective treatments for idiosyncratic facial pain.[11] Medications commonly prescribed for migraine prevention, such as valproate or topiramate, are often ineffective or poorly tolerated. Moreover, patients often are not candidates for such medications because they do not have a classic presentation of migraines.

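### Does the mix of 'and' and 'or' in the nasal-symptom-day endpoint (and a 0–10 versus 1–10 diary scale) leave that endpoint undefined?

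*Combined protocol and SAP*

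**What the plan says.** The nasal endpoint appears in four sections:

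- Section 1.4, endpoint column: "Change in average number of days per month with significant nasal congestion or rhinorrhea (defined as greater than 4/10".
- Section 1.4, objective column of the same row: "To evaluate the efficacy of erenumab in improving associated symptoms of nasal congestion and rhinorrhea".
- Section 1.1, secondary objectives: "Mean number of days per month with significant nasal congestion and rhinorrhea".
- Section 8.1: "To compare change in the mean number of days per month with significant congestion and rhinorrhea between treatment and placebo groups".
- Section 8.4.3: "Significant congestion and rhinorrhea will be defined as symptom score greater than 4 out of 10".

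On data collection, section 3.2.1 states that "subjects will be expected to score on a scale of 1 to 10 their symptoms of pain/pressure, nasal congestion, and rhinorrhea". Section 3.3 uses the same 1-to-10 range for the extra random-time pain rating. For the mean pain endpoint, section 8.4.3 has "The change in mean daily pain score (scale of 0 to 10) will be compared between the treatment and control groups". The diary form itself is not in the documents.

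**The concern.** The analysis section is where a programmer looks for the day rule, and 8.4.3 does not repeat the *or* from 1.4. Its wording refers to a symptom score in the singular although the diary lists two nasal symptoms. Three readings are possible: either score above 4, both scores above 4 on the same day, or two separate counts. They are different variables with different baselines. If the choice were left until after unblinding, it could be made with the results in view.

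The scale difference raises a smaller worry. A 1-to-10 diary has no stated value for a symptom-free day, while 8.4.3 treats mean pain as running from 0. If the scale altered which days exceed 4, it would reach the primary endpoint and the requirement in section 4.3 for 10 significant days in the lead-in.

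**Working it through.** **1. The plan's own figure.** The documents give no effect size, standard deviation or power for the nasal endpoint. The only figure is the primary sample size in section 8.2 (difference 3.0, SD 3.5, two-sided 0.05, 90% power, 10% dropout). By the normal approximation, n = 2 × (1.960 + 1.282)² × 3.5² / 3.0² = 28.6, so 29 per group, and 29 / 0.9 = 32.2, so 33. This matches the plan. An exact t calculation gives 30, then 33 or 34 depending on how the 10% is added. The nasal wording does not enter this calculation.

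**2. The texts side by side.** Only the endpoint column of 1.4 gives a connector and the threshold together in a form that can be programmed: count a day if congestion or rhinorrhea exceeds 4/10. The objective cell beside it describes the same endpoint with *and*. Within that one row, then, *and* names the two symptoms and *or* gives the day rule. Sections 1.1 and 8.1 are lists of objectives and comparisons, where the list sense is natural. Section 8.4.3 adds the threshold but nothing that requires both symptoms on one day.

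**3. How far the readings can differ.** For any subject and month:

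- either − both = days with exactly one symptom above 4;
- either + both = congestion days + rhinorrhea days.

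So *either* and *both* show the same change only if single-symptom days do not change. For illustration, let p₁ and p₂ be the daily probabilities of a score above 4 and r their correlation:

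P(both) = p₁p₂ + r√[p₁(1−p₁)p₂(1−p₂)], P(either) = p₁ + p₂ − P(both), each multiplied by 30 days.

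First row: P(both) goes from 0.16 to 0.09, which is −0.07 × 30 = −2.1. P(either) goes from 0.64 to 0.51, which is −0.13 × 30 = −3.9.

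| Assumed change (share of days) | r | Either | Both | Separate counts |
|---|---|---|---|---|
| Both symptoms 40% → 30% | 0 | −3.9 | −2.1 | −3.0, −3.0 |
| Both symptoms 40% → 30% | 0.7 | −3.27 | −2.73 | −3.0, −3.0 |
| Both symptoms 40% → 20% | 0 | −8.4 | −3.6 | −6.0, −6.0 |
| Both symptoms 70% → 60% | 0 | −2.1 | −3.9 | −3.0, −3.0 |
| 60% → 50% and 20% → 10%, rhinorrhea days all within congestion days | nested | −3.0 | −3.0 | −3.0, −3.0 |
| Congestion 40% → 30%, rhinorrhea stays 40% | 0 | −1.8 | −1.2 | −3.0, 0 |

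Every rate and correlation here is assumed. The gap can be zero, several days, or reversed in sign, so no single figure or bound describes it. These are also changes within one group. The documents give nothing from which to derive a between-arm difference for this endpoint.

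**4. The scale.** The cut-off applies to the recorded score, so moving the floor from 0 to 1 does not by itself change which recorded scores exceed 4.

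- If pain-free days are simply entered as 1, the rule is max(x, 1) and every day above 4 stays above 4. A group's mean pain rises by its pain-free days / 30. An arm with 3 to 9 more pain-free days per month (assumed) would have the between-arm difference in mean pain reduced by 3/30 to 9/30, that is 0.1 to 0.3 points.
- Moving the whole scale up one point is impossible at the top, because 10 would become 11.
- A stretched scale, 1 + 0.9x, could matter only at x = 4, giving 4.6, which might be entered as 5. This supposes that patients remap an unrecorded 0-to-10 score.

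**The case for a change.** The strongest case for a change is that 8.4.3 is the operative analysis text and leaves the rule open. If *and* is just a list, two separate counts is also a natural reading, and that still differs from the *or* in 1.4. The plan can be explicit when it wants components analysed separately, as it is for the MFIQ domains, but it is not explicit here. Secondary endpoints are tested by the primary method at three time points, with no multiplicity adjustment described, so an open day rule adds one more analytic choice. The remedy would be a sentence.

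Part of this stands. The wording is inconsistent, the readings are different variables, and nothing in the documents expressly bars a late choice. Two things limit it. The row labelled as the endpoint does state a rule, so an analyst who departed from it would be departing from the protocol. And because 3.2.1 lists congestion and rhinorrhea as separate items to score, every reading should be derivable from the same diary data. That is an inference, since the form is not shown.

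Section 2.2 groups the two among "secondary autonomic symptoms such as nasal congestion, rhinorrhea, tearing, and facial swelling". This makes positive correlation plausible and, in the first two rows of the table, correlation narrows the gap. It does not guarantee a small one.

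**Conclusion.** This is a clerical inconsistency in one secondary endpoint, and no change to the plan follows. The endpoint column of 1.4 provides a usable definition (a day counts if either symptom exceeds 4/10), and the same row shows that *and* is used loosely. Harmonising the wording would leave the sponsor free to pick any of the three rules and would correct no stated figure. An analyst who applies 1.4 obtains a valid randomised comparison.

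The scale difference is a probable wording slip, settled by whichever scale the form uses. If it only means that pain-free days are entered as 1, no pain-day count changes, and mean daily pain is affected by about 0.1 to 0.3 points under the assumed 3 to 9 extra pain-free days.

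This rests on three assumptions: the diary records the two nasal symptoms separately, both arms use the same form, and the 1.4 definition is the one followed. The nasal wording does not reach the primary endpoint, and no effect on sample size, power or the trial's conclusion has been shown.
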